#### 2.3 Benefit/Risk Assessment

engineered from commercially available IVIg. This increase in sialyation was demonstrated to increase anti-autoimmune and anti-inflammatory activity in preclinical pharmacological experiments. M254 has been evaluated in preclinical pharmacology and nonclinical toxicology studies. Intravenous immunoglobulin is considered standard of care in multiple disease settings notably in ITP. This study has been designed to start with Part A (Netherlands only) where ascending single doses of M254 will be evaluated for safety and tolerability in healthy individuals with all doses of M254 lower than doses considered safe in nonclinical toxicological studies. In Part B, patients with ITP will be administered a dose of M254, which has expected minimum biological activity, escalating up to clinical efficacious doses of increasing platelet counts. Part C will evaluate efficacious

Compound: M254 Protocol: MOM-M254-001

Protocol Date and Version:8 Global 28 April 2020

doses of M254 with crossover to standard of care IVIg. Patients in Part B and C will be assessed for the clinically relevant PD marker of increase in platelet count to identify dose to be evaluated in Part D.

It is expected that M254 will be biologically active at significantly lower doses compared to IVIg, so it is likely to shorten the infusion period without impacting expected efficacy when compared to IVIg in patients with ITP. All participants will be monitored for safety and tolerability as well as for efficacy (in parts with ITP patients) and only those ITP patients who are not at risk of life threatening bleeding with a platelet count  $\geq 15 \times 10^9/L$  will be selected.

Given the dose selection rationale described above, eligibility criteria, and active safety monitoring (including but not limited to platelet count assessment with potential of benefit of receiving same or more efficacious dose level), the study will not introduce unfavorable risk:benefit for the study participants.

For more detailed information on the potential risks and treatment of adverse events (AEs), please refer to the Investigator's Brochure [11].

### 3 OBJECTIVES AND ENDPOINTS

## 3.1 Part A (Netherlands only)

OBJECTIVES	ENDPOINTS
Primary	
To assess the safety and tolerability of a single ascending dose of intravenous administration of M254 in healthy volunteers	
 
Incidence and severity of adverse events         (AEs) following administration of M254         at single dose levels
 
Clinically significant changes in clinical         safety labs, vital signs, and         electrocardiograms (ECGs) with M254         administration
 

Secondary	
To characterize the pharmacokinetics (PK) of a single intravenous administration of M254 at different doses in healthy volunteers	Measurements of PK parameters of M254 following the administration of a single intravenous dose
Exploratory	
To characterize the pharmacodynamics (PD) of a single intravenous administration of M254 at different doses in healthy volunteers	Exploratory biomarkers relating M254 exposure to potential efficacy in autoimmune diseases and the M254 mechanism of action may be analyzed

Protocol Date and Version:8 Global 28 April 2020

# 3.2 Part B (USA sites included)

OBJECTIVES	ENDPOINTS
Primary	
To assess the safety and tolerability of a single intravenous administration of M254 in immune thrombocytopenia (ITP) patients compared to 1000 mg/kg intravenous immunoglobulin (IVIg)	
 
Incidence and severity of adverse events         (AEs) following administration of M254         at single dose levels and 1000 mg/kg         IVIg
 
Clinically significant changes in clinical         safety labs, vital signs, and         electrocardiograms (ECGs) following         M254 administration and 1000 mg/kg         IVIg
 

Secondary	
To characterize the pharmacokinetics (PK) of a single intravenous administration of M254 at different doses in ITP patients	Measurements of PK parameters of M254 following the administration of a single intravenous dose
Exploratory	
To characterize the pharmacodynamics (PD) of a single intravenous administration of M254 at different doses in ITP patients compared to IVIg	
 
Platelet response after M254         administration compared to IVIg
 
Exploratory biomarkers relating M254         exposure to potential efficacy in         autoimmune diseases and the M254         mechanism of action may be analyzed
 

Protocol Date and Version:8 Global 28 April 2020

## 3.3 Part C (USA sites included)

OBJECTIVES	ENDPOINTS	
Primary		

 
To assess the safety of a single intravenous administration of M254 compared to 1000 mg/kg of intravenous immunoglobulin (IVIg)
 
To characterize the PD of single intravenous administration of M254 compared to 1000 mg/kg IVIg
 
	Incidence and severity of adverse events (AEs) of M254 and 1000 mg/kg IVIg     Clinically significant changes in clinical safety labs, vital signs, and electrocardiograms (ECGs) following M254 administration and 1000 mg/kg IVIg	
	Platelet response after M254     administration compared to IVIg	
Secondary		
To characterize the pharmacokinetics (PK) of a single intravenous administration of M254 at different doses	Measurements of PK parameters of M254 following the administration of a single intravenous dose	
Exploratory		
To characterize the pharmacodynamics (PD) of single intravenous administration of M254 compared to 1000 mg/kg IVIg	Exploratory biomarkers relating M254 exposure to potential efficacy in autoimmune diseases and the M254 mechanism of action may be analyzed	

Protocol Date and Version:8 Global 28 April 2020

## 3.4 Part D (USA sites included)

OBJECTIVES	ENDPOINTS
Primary	
To assess the safety and tolerability of repeated intravenous administration of M254 in immune thrombocytopenia (ITP) patients	
 
Incidence and severity of adverse events         (AEs) with repeated administration of         M254
 
Clinically significant changes in clinical         safety labs, vital signs, and         electrocardiograms (ECGs) with M254         administration
 

Secondary	
To characterize the pharmacokinetics (PK) of repeated intravenous doses of M254 in ITP patients	Measurements of PK parameters of M254 following the administration of a repeated intravenous doses
To assess pharmacodynamics (PD) of repeated intravenous doses of M254 in ITP patients	Platelet response after repeated M254 administration

## 3.5 Hypothesis

No formal hypothesis testing will be used.

#### 4 STUDY DESIGN

#### 4.1 Overall Design

Compound: M254 Protocol: MOM-M254-001

Protocol Date and Version:8 Global 28 April 2020

for each cohort is provided in the pharmacy manual. More information can also be found in Section 6.1.1.1.

For Parts B, C, and D of the study, during the post-discharge follow-up period, participants may have laboratory assessments, vital signs, electrocardiogram (ECG), and PK samples assessed at home or another location mutually agreed with the site, but can be seen by the study staff if complications arise or for participant comfortability.

Subject enrollment in the USA will begin with Part B of this study. No subjects from the USA will be enrolled in Part A.

## 4.1.1 Part A (Netherlands only)

Part A is a single-ascending-dose, randomized, double blinded sponsor unblind, safety, tolerability, and PK assessment of M254 or placebo in 6 cohorts of healthy volunteers. Planned doses include 3, 10, 30, 60, 120, and 250 mg/kg. In Cohort 1, 5 subjects will be enrolled with 3:2 (active:placebo) randomization. In all other cohorts, subjects will be randomized 3:1 (active:placebo) with total of 4 subjects in each cohort. There will be approximately 25 subjects in Part A. Up to 2 additional cohorts may be added based on findings in prior cohorts. Additional dosing cohorts may be added on the recommendation of the SRC.

Following screening to confirm eligibility to participate, subjects will be randomized to receive M254 or placebo. Please refer to Section 4.3.1 and Figure 1-2 for dosing details.

At the first dose level (3 mg/kg), a sentinel group of 2 subjects (1 M254, 1 placebo) will be dosed and closely monitored for 48 hours before dosing the remainder of the cohort (2 M254, 1 placebo). The subjects in this sentinel group will be closely observed by the Investigator for any safety signals for the first 48 hours following drug administration. The general tolerability of the study drug will be monitored during this time and the ECG recordings and vital signs data will be reviewed. In addition, any reported AEs will be considered by the Investigator. If the safety and tolerability results of the first 48 hours following dosing for the initial subjects are acceptable to the Investigator, the other subjects of Cohort 1 of Part A may be dosed. There will be no additional sentinel groups in the study beyond this cohort (Cohort 1 Part A)

Safety assessments will be conducted out to Day 28 post M254 dosing. The SRC will review all available safety data after each cohort has completed at least 10 days of assessments after the single dose of M254. Dose escalation will only proceed after the recommendation of the SRC.

The SRC will review all safety data for all subjects in Part A out to Day 28. Cohorts in Part B may start before the completion of Part A; however, prior to initiation of any cohort in Part B, either the same or a higher dose level will have been given in Part A and have a positive recommendation by the SRC, with the exception of doses greater than 250 mg/kg.

Compound: M254 Protocol: MOM-M254-001

Protocol Date and Version:8 Global 28 April 2020

Dose escalation and continuation to the next study part may only occur when the SRC has given a positive recommendation and the Ethical Committee has given a statement of no objection, as per local requirement (where required).

Blood for safety labs and PK will be collected as defined in the Schedule of Activities (Table 1-1).

## 4.1.2 Part B (USA sites included)

Initiation of any cohort in Part B will only proceed on the recommendation of the SRC after safety data from Part A Cohort 4 at the 60-mg/kg dose level has been reviewed and confirmed by SRC.

Part B is a single-ascending-dose, fixed-sequence, open-label part to assess safety, tolerability, PK, and PD of M254 followed by 1000 mg/kg IVIg in approximately 4 cohorts of 2 ITP patients per cohort. Planned doses include 60, 120, 250, and 500 mg/kg. Up to 2 additional cohorts may be added based on findings in prior cohorts to better understand the safety of M254 and/or to better understand the efficacy to assist with dose selection for Part C. The maximum dose for Part B will not exceed 500 mg/kg. (The no-observed-adverse-event-level [NOAEL] of 1000 mg/kg was determined in the toxicology study in cynomolgus monkeys.) Additional patients to dosing cohorts may be added on the recommendation of the SRC.

Following screening to confirm eligibility to participate, patients will be dosed with M254. Please refer to Section 4.3.1 and Figure 1-3 for dosing details. There will be a 14-day safety monitoring period between enrollment of the first and second patients in the 500 mg/kg cohort.

Safety and platelet assessments will be conducted initially out to Day 28 post M254 administration. Patients will receive a fixed dose of IVIg at 1000 mg/kg on Day 29 if the patients' platelet count returns to  $\leq 15\%$  above baseline level. Patients whose platelets have not returned to  $\leq 15\%$  above baseline dosing level by Day 28 will have platelet determinations weekly until platelets return to  $\leq 15\%$  above baseline, up to 56 days postdose. If these conditions are not met by Day 57, IVIg will be administered, as long as the patients' platelets have returned to  $\leq 50 \times 10^9/L$ . If the platelets have not returned to  $\leq 15\%$  above baseline and are  $\geq 50 \times 10^9/L$ , the patient will complete Follow-Up assessments and be discharged from Part B. After dosing with IVIg, safety and the other assessments listed in the Schedule of Activities will be conducted for 28 days following IVIg administration.

The SRC will review all available safety data after each cohort has completed at least 10 days of assessments after the single dose of M254. Dose escalation will only proceed on the recommendation of the SRC after review of the safety data for each cohort (see Section 6.6). If 1 of the 2 ITP patients experiences any dose-limiting toxicity (DLT), the cohort will be repeated with 2 additional ITP patients either at the same or lower dose per the recommendation of the SRC. If at a given dose level, 2 patients (either 2 of 2 or 2 of 4) experience a DLT, that dose level will not be repeated, though a lower dose may be selected by the SRC.

Compound: M254 Protocol: MOM-M254-001

Protocol Date and Version:8 Global 28 April 2020

The SRC will review all safety data for all patients in Part B up to at least 28 days following M254 administration for the last patient. Initiation to Part C will only proceed on the recommendation of the SRC. Dose escalation and continuation to the next study part may only occur when the SRC has given a positive recommendation and the Ethical Committee has given a statement of no objection, as per local requirement (where required).

Blood for safety labs, PK, and PD will be collected as defined in the Schedule of Activities (Table 1-2).

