## (Schedule of Activities below is repeated when the patient receives their second infusion, which will be IVIg)

	Day	-28 to -2	-1 n	1 n	1	1	1	1	1	2	3 b	4 b	5 b	8±1 b	10 ±3	12 ±3 b	15 ±3 b	18 ±3 b	22 ±3 b	29 ±3 n
		Screening	Pre-infusion	Infusion							Post	-infusio	1							Follow-up
Procedure a	Hour		0	0	0 (end of infusion)	0.25	0.5	2	4	0	0	0	0	0	0	0	0	0	0	0
Discharge from	Study																			$X^p$

ADA = anti-drug antibody; AE = adverse event; ECG = electrocardiogram; HBsAg = hepatitis B surface antigen; HCV = hepatitis C virus; HIV = human immunodeficiency virus; IgG = immunoglobulin G; ITP-BAT = immune thrombocytopenic purpura bleeding assessment tool; IV = intravenous; PK = pharmacokinetics.

- Procedures should occur in the order presented above from top to bottom if more than 1 procedure occurs at the same nominal time. Urine sampling or anything with a specific footnote may be done out of order.
- Only visits required to be at the study site are screening, infusions, the day after infusion, Day 10 after M254 infusion (as this is last safety visit prior to dose escalation decision), and Day 29, all others can be done by visiting nurse if patient prefers this option. Visit windows of ±1 day should be used whenever possible; ±3 day windows shouldonly be used when required due to clinical site closures (eg, for holidays or COVID-19-related limited schedules). When visit windows overlap, they must not be combined into a single actual day. Note: the first patient in the 500 mg/kg cohort must be seen in clinic at the Day 15 visit as there will be a 14-day safety monitoring period between enrollment of the first and second patients in the 500 mg/kg cohort.
- Screening weight will be used to determine eligibility and dosing, and will allow up to 1 month for weight variability.
- d Vital signs includes body temperature, supine (after 5 minutes) blood pressure, pulse rate, and respiratory rate. Vital signs will be assessed every 30 minutes during an infusion. For infusions <35 minutes, vital signs assessments may occur just after starting the infusion and just prior to the end of the infusion. Refer to Footnote t for exception.
- c Telemetry should start at or before beginning of the M254 infusion and stop at or after end of infusion. Telemetry does not need to be performed during the IVIg infusion.

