## **6.6** Dose-Cohort Study Escalation Rules

In this study, Parts A and B are dose-escalating; Parts C and D are not dose-escalating.

A dose escalation report (DER) will be provided by the Investigator to the Independent Ethics Committee (IEC) (where required) following completion of each dose level. The SRC will approve escalation to the next dose only if none of the stopping criteria have been reached, the safety and tolerability (and PD for Part B) out to Day 10 are acceptable, and there are no concerns regarding delayed significant AEs in earlier cohorts.

The minimum number of participants required to decide on dose escalation is 2 participants on active treatment (ie, a total of at least 3 subjects in Part A at all dose levels; and 2 patients in Part B); in Part B for dose levels precedented as tolerated with safety reviewed in Part A, only 1 subject is required for dose escalation though 2 will remain planned for the cohort.

Based on absence of significant toxicity in the Good Laboratory Practice (GLP) toxicity studies, escalation to the next higher dose will be up to approximately CCI. Based on emerging safety data (and PD data in Part B), lower or other intermediate dose(s) may be used, for instance when anticipated that after a planned dose escalation stopping criteria will be met. Pharmacokinetic data is not deemed necessary for dose escalation since IV dosing of this modified IgG has predictive exposures (100% bioavailability, volume of distribution [Vd] and clearance expected to be similar to endogenous IgG). There are no significant toxicity findings in the preclinical studies, and the maximum exposure in healthy volunteers is expected to remain well below exposures of the high dose (1000 mg/kg) used in GLP toxicity studies. In patients the maximum exposure is not expected to be above the high dose (1000 mg/kg) used in GLP toxicity studies.

Compound: M254 Protocol: MOM-M254-001

Protocol Date and Version:8 Global 28 April 2020

A more conventional 3+3 escalation design was considered but not employed in this study. A notable difference between the expectation of the design in the current study with 2 patients compared to a 3+3 design in literature is how the dose is used in the future. In the current study, [CC]

In a more conventional 3+3 design, a dose that triggers the 3+3 rule would be considered **tolerable**, and would be used for future study.

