## 6.7 Stopping Rules

## 6.7.1 Dose-Cohort Study Stopping Rules

Dosing within a cohort and dose escalation to a next cohort will be halted pending evaluation by Sponsor and SRC recommendation if 1 of the following circumstances occurs and it is determined by the Investigator that the occurrence is possibly related to the administration of study drug:

- A serious adverse reaction (ie, a SAE considered at least possibly related to the study drug administration) in 1 subject.
- Grade 3 or higher AE per National Cancer Institute (NCI) CTCAE version 5.0 criteria (ie, severe nonserious AEs considered at least possibly related to the study drug administration) in 2 participants in the same cohort, or in 1 subject in the sentinel cohort.
- Grade 4 or higher grade AE per NCI CTCAE version 5.0 criteria.
- Other findings that, at the discretion of the Investigator in consultation with Sponsor's Medical Monitor and SRC recommendation, indicate that further dosing should be stopped.

When stopping rules for a cohort are met, the randomization code for participants meeting the stopping rules will be unblinded. If after de-blinding it is concluded that participants on active medication meet the stopping rules, dosing in the cohort will be stopped and no further dose escalation will be performed.

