## **6.7.2 Dose Limiting Toxicities**

Dose-limiting toxicities will include any NCI CTCAE v.5 Grade 3 or higher adverse reaction occurring within 4 weeks following the administration of M254.

**Note:** Events considered by the sponsor as clearly unrelated to the study drug will not be considered a DLT, eg, thrombocytopenia related to ITP, accidents, and lab results attributed to other therapies or illnesses.

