# 6.7.3 Rules for Dosing Adjustments, Withholding or Restarting, Permanent Discontinuation

Unless participant safety precludes doing so, the Medical Monitor should be consulted prior to stopping or modifying the dosing schedule of study drug.

Compound: M254 Protocol: MOM-M254-001

Protocol Date and Version:8 Global 28 April 2020

If more than 1 subject or patient with CTCAE Grade 3 or 4, not reasonably related to an alternative etiology (eg, motor vehicle accident-related injury or gunshot wound) the sponsor will discuss already collected data from the healthy subjects in Part A prior to discontinuation for the Part A (if already more than 1 dose level has been evaluated prior to the Part A being discontinued) with the Investigators and may modify other parts of the study as needed.

If 1 of the 2 ITP patients in Part B experiences any DLT, the cohort may be repeated with 2 additional ITP patients either at the same or lower dose per the recommendation of the SRC. If at a given dose level, 2 patients (either 2 of 2 or 2 of 4) experience a DLT that dose level will not be repeated, though a lower dose may be selected by the SRC.

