## 6.7.4 Study Stopping Rules

Dosing in the study will be halted pending evaluation by Sponsor and SRC recommendation if one of the following circumstances occurs:

- Grade 5 AE considered related to study treatment, in which case the review process will also include regulatory agencies and IRBs/Ethics Committees
- The following Grade 3 or greater treatment-related AE in 2 or more patients:
  - thromboembolic AE
  - renal impairment AE
  - hemolysis AE
  - creatinine elevation

NOTE: Events that are definitely not related to study treatment (eg, accidents or other external causes) will not trigger study-stopping rules.

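### After 1 DLT in 2 Part B patients, Protocol 4.1.2 requires a repeat cohort and 6.7.3 only permits one; if that DLT is a single non-serious Grade 3 reaction found late, pausing a higher cohort already open is left to SRC discretion

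*Protocol*

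**What the plan says.** Part B of the protocol escalates M254 through planned cohorts of two ITP patients at 60, 120, 250 and 500 mg/kg. The provisions that bear on a DLT are these.

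- **Repeat rule, first statement (4.1.2).** After a DLT in 1 of 2 patients, "the cohort will be repeated with 2 additional ITP patients either at the same or lower dose per the recommendation of the SRC".
- **Repeat rule, second statement (6.7.3).** For the same event, "the cohort may be repeated with 2 additional ITP patients either at the same or lower dose per the recommendation of the SRC".
- **DLT definition (6.7.2).** Any "Grade 3 or higher adverse reaction occurring within 4 weeks following the administration of M254", except events the sponsor considers clearly unrelated.
- **Earliest escalation review (4.1.2, 6.6, Table 1-2).** The SRC can review after at least 10 days of assessments. A Table 1-2 footnote lists among the on-site visits "Day 10 after M254 infusion (as this is last safety visit prior to dose escalation decision".
- **Minimum number to escalate (6.6).** Two patients in Part B, but at dose levels already tolerated and reviewed in Part A "only 1 subject is required for dose escalation though 2 will remain planned for the cohort".
- **Cohort halt (6.7.1).** One related serious event, a related Grade 4 or higher event, or related Grade 3 or higher events "in 2 participants in the same cohort, or in 1 subject in the sentinel cohort". There is also a discretionary clause for other findings.
- **Study halt (6.7.4).** A related Grade 5 event, or "The following Grade 3 or greater treatment-related AE in 2 or more patients", followed by a short list of event types.
- **Spacing at the top dose (4.1.2).** A "14-day safety monitoring period between enrollment of the first and second patients in the 500 mg/kg cohort".

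The synopsis account of Part B and the SAP's design section state no DLT rule, so neither settles which version of the repeat rule governs.

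**The concern.** The two statements of the repeat rule are almost word for word the same except for the verb, and the verb decides whether two more patients are treated. A site or SRC working from 4.1.2 must treat them; one working from 6.7.3 may decide without them. The SRC's judgement after a DLT could then rest on two Part B patients instead of four. Both sections also carry a rule for 2 DLTs in 4 patients at a dose level, which can only come into play if the repeat is done at that level.

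The second issue is timing. DLTs count for 4 weeks, but the next cohort can open on Day 10 data, and on one Part B patient at doses with Part A precedent. A DLT that appears after Day 10, or in the second patient of the lower cohort, can therefore surface while patients are being dosed at the next level. At stake is whether anything stops dosing at that higher level until the event has been looked at.

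**Working it through.** Part B has no formal sample size calculation (9.1) and the plan states no operating characteristics for its DLT rule, so there is no figure to reproduce. The check is a trace through the rules, then simple arithmetic.

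**Step 1. Trace one related, non-serious Grade 3 reaction in Part B through each visible rule.**

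| Rule | What it needs | Met? |
|---|---|---|
| 6.7.1, serious event | 1 related serious event | No |
| 6.7.1, Grade 4 or higher | 1 related event | No |
| 6.7.1, Grade 3 or higher | 2 participants of one cohort, or 1 in the sentinel cohort | No; 4.1.1 confines sentinels to Part A Cohort 1 |
| 6.7.3, data discussion | more than 1 participant with Grade 3 or 4 | No |
| 6.7.4 | Grade 5, or listed events in at least 2 patients | No |
| 6.7.1, other findings | discretion | Discretionary |
| 8.3.5 | moderate or severe systemic infusion reaction | SRC meeting, only if it is an infusion reaction |
| 4.1.2 and 6.7.3 | 1 DLT in 2 patients | Yes, with conflicting instructions |

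For this event, the two repeat sentences are the only visible rule specific to DLTs.

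**Step 2. How often the conflict would arise.** The documents give no DLT rate, so p is an assumption.

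- Exactly 1 DLT in 2 patients: 2p(1 − p).
- At least 1 further DLT in 2 more patients at the same dose: 1 − (1 − p)².

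| Assumed p | Exactly 1 of 2 | Further DLT in the repeat pair |
|---|---|---|
| 10% | 2 × 0.1 × 0.9 = 18% | 1 − 0.9² = 19% |
| 20% | 2 × 0.2 × 0.8 = 32% | 1 − 0.8² = 36% |
| 30% | 2 × 0.3 × 0.7 = 42% | 1 − 0.7² = 51% |
| 50% | 2 × 0.5 × 0.5 = 50% | 1 − 0.5² = 75% |

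**Step 3. How much of the DLT window follows the earliest review.** In days: (28 − 10)/28 = 18/28 = 64%. In Table 1-2 the safety-lab visits after Day 1 are Days 2, 4, 8, 15, 22 and 29, so 3 of 6 fall after Day 10. These are shares of calendar time and visits, not of risk.

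Let f be the share of DLTs that fall after Day 10, also not given. The chance of exactly one DLT in the pair, falling late, is 2p(1 − p)f. For f from 10% to 64% (the latter being uniform timing):

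- p = 10%: 0.18 × 0.10 = 1.8% to 0.18 × 18/28 = 11.6%
- p = 20%: 0.32 × 0.10 = 3.2% to 0.32 × 18/28 = 20.6%

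These include serious and Grade 4 or higher DLTs, which 6.7.1 already halts, so they overstate the narrow gap.

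**Step 4. The top dose.** 500 mg/kg is the only planned Part B dose not planned in Part A. With no review delay, its first patient could be dosed about 10 days after a 250 mg/kg patient, and its second at 10 + 14 = 24 days. Both fall inside that patient's 28-day window. A review longer than 28 − 24 = 4 days moves the second one outside it. The 14-day gap runs from enrollment of the first 500 mg/kg patient; a late DLT at 250 mg/kg does not trigger it.

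**The case against.** A reader might infer that the plan takes no automatic action for any DLT found after the next cohort opens. The documents do not support that. The 6.7.1 halt has no time limit and covers a related serious event, a related Grade 4 or higher event, and related Grade 3 events in two participants of a cohort; if confirmed on active drug, escalation ends. The repeat rule in 4.1.2 has no Day 10 cut-off. Section 6.6 also makes the absence of concern about delayed significant events in earlier cohorts a condition for approving the next dose, so late events were anticipated. All of this stands. What it leaves open is a single non-serious Grade 3 DLT: the 6.6 condition governs approval of a further dose level, not the conduct of one already open.

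A reader might also infer that 6.7.3 permits escalation after a DLT without a repeat. It does not; the SRC must still approve every escalation.

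It can be argued that the verbs hardly matter, since both sentences defer to the SRC. In 4.1.2, however, that phrase reads most naturally as governing the choice between the same and a lower dose, not whether to repeat.

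Reviewing from Day 10 is a deliberate, disclosed choice, and where one Part B patient suffices, Part A subjects at that dose also inform the decision; Part A is reported complete in the synopsis. The dose escalation report and, where required, the ethics no-objection statement add time that Step 4 ignores. For infusion reactions, 8.3.5 places most within 24 hours and most delayed ones at 5 to 10 days, so the late share is probably well below 64%. These points reduce the size of the timing gap without closing it.

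Finally, part of 6.6, including the sentence on how doses are used in this two-patient design, is redacted. It may bear on this, so the conclusion is limited to the visible text.

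**Conclusion.** The concern holds in a limited form. Sections 4.1.2 and 6.7.3 contradict each other on a dose-escalation safety rule, and nothing else visible resolves it. For a single related, non-serious Grade 3 DLT, no numeric trigger makes the contradiction moot. If that DLT is found in a lower cohort while a higher one is open, a pause of the higher cohort depends on SRC discretion.

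The conflict would arise in 18% to 50% of two-patient cohorts under assumed DLT rates of 10% to 50%. The 19% to 75% chance of a further DLT applies only to a repeat at the same dose. It measures what the SRC would not learn if an optional repeat were skipped; it should not be read as a probability of unsafe escalation. The timing figures rest on assumed rates and an assumed late share, and are upper-end for the events in question.

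The wording should be corrected. The point does not show that the escalation scheme as a whole is unsafe.

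**What to change.** 1. In 6.7.3, replace *may* with *will* in the repeat sentence, to match 4.1.2.
2. Add to both 4.1.2 and 6.7.3: *If a DLT within 4 weeks of dosing is reported at a lower dose level after a higher cohort has opened, no further patient is dosed at the higher level until the SRC has reviewed it.*

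A rule that clears escalation once two repeat patients reach Day 10 is not advisable. It would reproduce the mismatch between Day 10 and 4 weeks, and would create a path upward after 1 DLT in 4 that might conflict with the redacted part of 6.6.

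The cost is protocol wording and, when the rule is used, one SRC review, a short delay, and up to 2 more patients per repeat. The 8 optional expansion patients in 4.1.6 cover 8/2 = 4 repeats within the planned total of about 20 (8 in planned cohorts + 4 in optional cohorts + 8 in expansions), provided they are not used for other purposes.
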